c. Statistical plan including sample size justification and interim data analysis.

Sample Size: As a pilot RCT, we aim to enroll a convenience sample of ~1.5 patients/month, for a total of 54 patients (based on 36 months of recruitment; see Timeline-Candidate Statement). Extensive experience enrolling ARF patients in prior studies by our group^{10,121,125-127} suggests this rate is feasible for a K-23 award at this study site. We expect an overall <15% missing completion rate due to mortality and loss to follow-up (in our prior study of >500 ARF survivors, loss to follow-up was 2% with 7% mortality at 6 months¹²⁵), thus, we expect 54 patients to complete the intervention. With 54 participants (27 in each group), assuming 5% alpha, 80% power and HAD SD of 4.2 points based on our prior research in ARF survivors^{89,90}, for our secondary aim of efficacy, we can detect a 3.1 point difference in HADS score between the 2 treatment groups, which approximates HAD's 2.9 point minimum important difference (MID) in ARF survivors.¹²⁸ This proposed enrollment rate and sample size is consistent with existing pilot/feasibility trials in ARF research.^{101,129,130}

Statistical Analysis

Hypothesis 1a: *A 12-week BA-R intervention in ARF survivors will be feasible, as demonstrated by an average accrual rate of 1.5 patients per month, completion of ≥80% of the intervention phone calls, and ≤15% of enrolled patients lost to follow-up for outcomes assessments at end of the 12-week intervention.* We will assess the total number of intervention phone calls completed per patient as a proportion of the number of intervention phone calls each patient is intended to complete (i.e., 9 intervention calls – weekly during first 6 weeks and bi-weekly for second 6 weeks of the 12-week protocol). We also will assess total number of intervention phone calls completed by all study participants as a proportion of total intervention phone calls expected in the study. We will calculate the number of patients completing the 12-month follow-up session as a proportion of the number of patients enrolled to measure loss to follow-up.

Hypothesis 1b: *At the end of the 12-week BA-R intervention, ARF survivors in the BA-R versus “usual care” group will demonstrate decreased depressive symptoms, less impairments in physical function and quality of life, and reduced healthcare utilization.* Analyses will follow a modified intention-to-treat principle and a 2-tailed p<0.05 is statistically significant. Patient mortality is expected to occur infrequently (see Sample Size above) and not to differ by treatment vs. control group; therefore, all analyses will be conducted for 12-week survivors only. The analysis will include separate comparisons of the effect of the BA-R intervention vs usual care control on each of the blinded outcomes in Table 4. These analyses will estimate the average treatment effect, i.e. the difference in the mean 12-week outcome comparing the BA-R intervention to the usual care control, using the precise locally efficient augmented simple estimator (PLEASE) described in Colantuoni and Rosenblum[REF: 135]. This method for estimating the average

treatment effect is similar to the analysis of covariance (ANCOVA) approach in that it incorporates the baseline outcome (if measured) which, if correlated with the 12-week outcome, can improve the precision of the estimated average treatment effect [Ref 134]. This method also accounts for more general patient drop-out models than the ANCOVA approach. Specifically, the ANCOVA approach is valid under completely at random drop-out, whereas the PLEASE is valid under missing at random drop-out, i.e. when patient drop-out differs by treatment group or across levels of the baseline outcome or other measured variables at baseline. The PLEASE requires a priori specification of three models: an outcome regression model (fit separately for each treatment group) that will include age, gender and the baseline outcome (if measured), a propensity score model that will include age, gender and the baseline outcome (if measured) and a drop-out model (fit separately for each treatment group) that will include age, gender, and the outcomes measured at baseline (HADS, Brief Cope, CD RISC, BADS). As exploratory analyses, the 12-week outcomes (e.g. HADS scores) will be summarized (summary statistics including counts of missing values and histograms) and the correlation of the baseline (if appropriate) and 12-week outcomes will be computed, separately by treatment arm. Patient mortality, drop-out and missing data will be described for all variables, separately for treatment vs control groups. Patient characteristics will be compared between those with vs. without missing outcomes (due to drop-out and missing values).¹³⁶⁻¹³⁸

A series of secondary analyses will be conducted to improve our understanding of the changes in the outcomes over time under the BA-R intervention and usual care control and to improve the design of subsequent larger randomized trials evaluating the effect of the BA-R intervention. Specifically, the outcomes over time within each treatment group will be visualized using spaghetti plots to display each patient's data with the mean outcome over time trajectory over time highlighted. Longitudinal linear regression models for the longitudinal outcomes (i.e. baseline, 6-week and 12-week outcomes) will be constructed that account for time (factor), treatment and the interaction of treatment and time. These longitudinal models will be fit using weighted least squares and will allow for the possibility that the variance in the outcomes can change over time and that outcomes measured on the same patient over time may be correlated. In addition, we will explore the prognostic ability of other baseline variables (e.g. age, sex and history of depression) for the 12-week outcomes using the method described by Colantuoni and Rosenblum.¹³⁵ Specifically, we will compute the leave-one-out cross-validated relative R-square which compares the R-square obtained when modeling the 12-week outcomes as a function of selected baseline variables, separately for each treatment arm, to that obtained by predicting the 12-week outcomes with the treatment arm specific mean. The statistic ($1 - 1/\text{relative R-square}$) is roughly the sample size reduction that can be achieved if the selected baseline variables are incorporated into an adjusted treatment effect estimator compared to using an unadjusted estimator. This assessment will provide relevant information to improve the design and analysis of subsequent larger randomized trials evaluating the effect of the BA-R intervention; specifically, by informing which additional prognostic baseline variables to include in the ANCOVA approach described above to further improve the precision of the estimated treatment effects.

Hypothesis 1c: We will conduct qualitative research, using thematic analysis, to identify key barriers and facilitators to engaging with the BA-R intervention, as well as perceived satisfaction, acceptability and feasibility of BA-R. All interviews will be audio recorded using a digital recorder and subsequently transcribed on a rolling basis. Using a data-driven approach, the first five interviews and associated interviewer field notes will be independently read by [name] and a second coder with expertise in qualitative research methods. The data will be segmented by identifying information pertinent to the research question then categorizing and giving identifying names (codes) to the patterns that emerge. Following the review of the five initial interviews, the two investigators will meet to discuss common findings and key themes. A code book will then be developed to guide the analysis of the transcripts through an iterative process of discussion and review. Transcripts will be reviewed on an ongoing basis to identify when thematic saturation is reached, defined by at least 3 interviews without additional information. Nvivo software will be used to organize the data for analysis. Coding will be compared

between the coders using percentage agreement and Cohen's kappa coefficient. Discrepancies will be reviewed and resolved through discussion between reviewers and a third review, if needed.

Hypothesis 2a: *Increased resilience, adaptive coping, and social engagement are associated with fewer depressive symptoms using the combined patient cohort from the BA-R and control groups in Aim 1.* Our primary outcome is depressive symptoms from the Hospital Anxiety and Depression Scale (HADS). First, descriptive statistics (i.e. mean, standard deviation, histograms) will be performed for the baseline HADS and the exposure and confounding variables. Next, a bi-variable analysis will be conducted for the HADS vs the baseline exposure variables for Aim 1 (i.e., CD-RISC 10, Brief COPE, BADS) using linear regression. In multivariable analyses, we also will include potential confounding variables (Table 1), including no more than 4 covariates in each model to avoid overfitting with sample size 54 (after accounting for mortality and loss to follow-up). These analyses will be conducted for all patients in the combined cohort in Aim 1.

Hypothesis 2b: *At the end of the 12-week intervention, ARF survivors in the BA-R versus “usual care” control group will demonstrate improvements in coping, resilience and social engagement.* Analyses for the comparison between the intervention and usual care groups will follow a modified intention-to-treat principle, with a 2-tailed $p < 0.05$ is considered significant. Analysis will include separate comparisons of the intervention vs control for each of outcomes (Brief Cope, CD RISC, BADS), in accordance with the description above for Hypothesis 1b.

Hypothesis 2c: *We will conduct qualitative research, using thematic analysis, to identify the role of resilience, coping, and social engagement in recovery from ARF.* See analysis plan above for Hypothesis 1c. This analysis will include all patients in the combined cohort from Aim 1.

Hypothesis 3: *The HADS and PHQ-8 will adequately discriminate depressive symptom severity vs. the SCID-5 “gold standard” using the combined patient cohort from the BA-R and control groups in Aim 1.* All analyses will be conducted using only the 12-week outcomes data. The RCT inclusion criteria (in Aim 1), which establish the patient cohort for Aim 3, include only patients with PHQ-2 ≥ 2 (i.e., at least mild depressive symptoms). Therefore, for Aim 3 analyses, we will categorize depressive symptoms based on severity category for the SCID-5 (mild vs moderate to severe). We will then examine the screening characteristics of HADS and PHQ8 total scores vs the SCID-5 using a receiver operating characteristics (ROC) curve, including the area under the ROC curve (AUC), and sensitivities, specificities, and positive and negative predictive values at each HADS and PHQ8 total-score cut point. Our sample size (N=54 patients) is adequate to permit an assessment of criterion validity that is rated, at least, as “good” quality according to the COSMIN standard for psychometric analyses.¹³¹ In addition to assessment of criterion validity, we will assess internal consistency of the PHQ-8 using Chronbach’s alpha, with a result of ≥ 0.7 and < 0.95 indicating “good” quality as per COSMIN¹³² (HADS has an existing publication demonstrating good internal consistency in ARF survivors so no such analysis will be repeated for HADS)¹³³.

d. Early stopping rules.

There will be no interim analyses to determine early stopping for efficacy or futility with respect to the main efficacy hypothesis. The primary outcome for this study is feasibility.

8. Risks

a. Medical risks, listing all procedures, their major and minor risks and expected frequency.

1) Depression: Participants will be asked questions about depression using the PHQ-8, HADS and the SCID. While asking questions, we may detect that the patient has worsening depressive symptoms.

2) Breach of confidentiality: We will be collecting data about the participant, and hence, there is a risk of breach of confidentiality.

b. Steps taken to minimize the risks.

[figure not shown]
Depression (PHQ-8, HADS and SCID): All potential participants who have worsening depression symptoms will be informed that they may be depressed and advised to consult with their health care provider.

If there is any potential concern regarding safety of a participant, a physician on our study team will become involved. The research assistant will be instructed to take the steps outlined in Figure 2 below.

- Complete a Serious Adverse Event Report (SAE) form documenting the outcome of this questionnaire and subsequent action taken.
- If unsure about the patient's risk, contact a study physician to notify them immediately and discuss action to take.

Figure 2. Suicide Risk Management Protocol

Suicide Risk Management Protocol for BA-R Pilot Study

Adapted from Suicide Risk Management Protocol in Post-Cardiac Arrest Survivors: Development, Feasibility, and Outcomes by RA Bucy et al Ann Am Thorac Soc. 2016 Dec 16; Article in Press)

*Suicide prevention helpline by state:

State Number	Local County/City wise
Maryland [name] http://www.suicide.org/hotlines/maryland-suicide-hotlines.html	
 • Baltimore • Baltimore Crisis Response- [contact] • Suicide Prevention [contact] • Columbia [contact] • Frederick [contact] • Glen Burnie (Serving Baltimore County) [contact] • Hyattsville (Serving Anne Arundel, Calvert, Charles, Montgomery, Prince George's & St. Mary's Counties) [contact] • Rockville [contact] [contact] TTY • Salisbury [contact](HELP) [contact]
Washington D C [name] (Arlington)	
 • Arlington [contact]
Virginia [name] For DC Metropolitan area http://www.suicide.org/hotlines/virginia-suicide-hotlines.html	
 • Arlington [contact] • Dumfries[contact] • Richmond [contact] • Roanoke[contact] (8:15 am to midnight) • Winchester [contact]

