A single cohort of patients will be used for all 3 Aims (i.e. both intervention and control groups recruited into the randomized controlled trial (RCT) will form a single cohort for analyses in Aims 2 and 3). We will enroll 54 patients from all Johns Hopkins Hospital adult ICUs. If patients are lost to follow-up, we will enroll up to 10 additional patients to obtain 12-week outcomes assessments on a total of 54 patients (27 in each group). Oral informed consent will be obtained from all participants.

Aim 1 Methods: We will conduct a single-site, pilot RCT (N=54) evaluating the feasibility (primary objective) and efficacy (secondary objective) of a 12-week behavioral activation-rehabilitation (BA-R) intervention versus “usual care”, in acute respiratory failure (ARF) survivors. We will evaluate the BA-R intervention via an RCT study design, with blinded outcome assessments. We will test the feasibility of this intervention (primary outcome) and its efficacy (secondary outcome) at the end of intervention. Figure 2 shows study timeline.

[figure not shown]
After return home, consented patients will be randomized to: (1) behavioral activation and rehabilitation (BA-R) intervention or usual care. Randomization will occur via web-based tool, using variable-sized

blocks from 2 to 4, and stratified by history of depression prior to ICU admission (based on chart review and patient interview). Baseline variables are detailed in Table 1 below.

Table 1: Baseline Variables

Variable	Collection	Measurement Scale
Patient Variables		
Age/sex/race	Chart review	Continuous/Binary/Categorical
Education (number of years/highest attainment)	Patient interview	Continuous/Categorical
Employment & Health Insurance status	Patient interview	Categorical
Comorbidity indices: Charlson (CCI) ^a & Functional (FCI) ^b	Chart review	Ordinal
Alcohol intake/misuse / Drug abuse	Chart review	Categorical
Physical function at baseline: AMPAC-CAT ^{87,88 c}	Patient interview	Continuous
ICU and Hospital Variables		
ICU admission diagnosis (e.g., sepsis, renal failure)	Chart review	Categorical
Severity of illness: APACHE II ^d	Chart review	Continuous
Benzodiazepine use and dosing ^{56,89,90}	Chart review	Continuous
Daily ICU Sedation Status: RASS ⁹¹	Chart review	Ordinal
Daily ICU Delirium Status: CAM-ICU ^{92,93}	Chart review	Categorical
Daily Minimum Glucose ⁹⁰	Chart review	Continuous
ICU and Hospital Length of Stay	Chart review	Continuous

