Participants cannot be blinded to the intervention. Treatment allocation will be concealed, except to staff performing the intervention. Research staff performing all outcome assessments will be blinded (except [name] who will not be masked to treatment assignment and will administer the SCID). Patients will be instructed (using standard language, as per prior research)¹⁰¹⁻¹⁰³ not to discuss treatment allocation with staff prior to each assessment. Adequacy of blinding will be assessed by asking assessors to indicate if they were un-blinded and for their “best guess” of patients’ treatment allocation.¹⁰³

d. Justification of why participants will not receive routine care or will have current therapy stopped.

All study participants in the usual care group will receive routine care. Participants in the intervention group will receive the intervention in addition to routine care.

e. Justification for inclusion of a placebo or non-treatment group.

We chose to compare our intervention against a “usual care”, rather than a sham control that would attempt to control for extra attention but does not represent real-world usual care. We will measure usual care for both control and intervention groups (Table 2). Participants in the usual care group will not be deprived of any known potential benefits by not being included in the intervention group (no proven benefit yet in the ARF population).

f. Definition of treatment failure or participant removal criteria.

Participants will only be removed from the study if they withdraw consent.

g. Description of what happens to participants receiving therapy when study ends or if a participant’s participation in the study ends prematurely.

If a participation in the study ends prematurely, the participant will continue to receive usual care. Ending the intervention prematurely does not pose any harm to the participant.

5. Inclusion/Exclusion Criteria

Table 3. Eligibility Criteria

Inclusion Criteria:

≥18 years old

Living at home before the current admission (not in a facility)

Acute respiratory failure managed in the ICU ≥ 24hrs (≥1 of the following):

- 1) Mechanical ventilation via an endotracheal tube or tracheostomy > 12hrs (and not ventilator-dependent before admission) OR
- 2) Non-invasive ventilation (CPAP, BiPAP) > 4 hours in a 24 hour period provided for acute respiratory failure (not for OSA or other stable use) OR
- 3) High flow nasal cannula with FiO₂ ≥ 0.5 for ≥4 hours in a 24hr period

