At least mild depressive symptoms (score ≥2 on PHQ-2 scale⁴⁶)

Exclusion Criteria:

Pre-existing cognitive impairment (based on review of medical records, or proxy-administered IQ-CODE¹⁰⁴ score >3.3)

Declines informed consent or not capable of providing informed consent

Non-English speaking

Homelessness

Bedbound prior to the current admission

Expected survival < 6 months according to ICU attending

ICU LOS > 30 days

Not discharged home from the hospital

Complex medical care expected soon after discharge (e.g. multiple planned surgeries, transplantation evaluation, extensive travel needs for hemodialysis, chemotherapy or radiation therapy, etc)

Active substance abuse or psychosis

Pregnancy

Suicidality

Incarcerated

Lack of access to telephone or inability to use telephone independently

Pregnancy

Suicidality

6. Drugs/ Substances/ Devices

N/A

7. Study Statistics

a. Primary outcome variable.

The primary outcome variable is feasibility. We will assess the total number of intervention phone calls completed per patient as a proportion of the number of intervention phone calls each patient is intended to complete (i.e., 9 intervention calls – weekly during first 6 weeks and bi-weekly for second 6 weeks of the 12-week protocol). We also will assess total number of intervention phone calls completed by all study participants as a proportion of total intervention phone calls expected in the study (i.e., 9 calls/patient x 27 intervention patients = 243 calls). We will calculate the number of patients completing the 12-week follow-up session as a proportion of the number of patients enrolled to measure of loss to follow-up.

b. Secondary outcome variables.

Hospital Anxiety and Depression Scale (HADS)⁴⁵: The HADS (Tables 1 and 4), separately assesses depressive and anxiety symptoms in a wide variety of patients, is valid, reliable^{45,56,65,105,106} and highly correlated with psychiatric evaluation in other populations,¹⁰⁷ but never validated in ARF survivors. A HADS score ≥8 indicates clinically important depressive symptoms. Scores of 8-10 indicates “mild” symptoms, 11-14 “moderate”, and ≥15 “severe”. HADS is the most commonly used measure of depressive symptoms in ARF survivors^{10,56,108} and is considered to be particularly appropriate in ARF patients because

HADS does not emphasize the physical symptoms of depression that may be confounded by post-ARF physical morbidity.

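### The study-level call-completion rate uses 243 expected calls, which is too few if additional patients take the BA-R arm above 27 (minor)

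*Combined protocol and SAP*

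**What the plan says.** Section 7a sets two call measures as part of the feasibility outcome. The first is each patient's completed calls out of the nine intended. The second is the "total number of intervention phone calls completed by all study participants as a proportion of total intervention phone calls expected in the study", and a bracket opened by 'i.e.' gives the expected total as "9 calls/patient x 27 intervention patients = 243 calls". The sentence after that measures loss to follow-up by the "number of patients completing the 12-week follow-up session as a proportion of the number of patients enrolled".

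Section 4a (Overview of Research Methods) gives the base enrolment: "We will enroll 54 patients". It then provides for replacing patients whose follow-up is lost, in these terms: "we will enroll up to 10 additional patients to obtain 12-week outcomes assessments on a total of 54 patients (27 in each group". Section 4f adds: "Participants will only be removed from the study if they withdraw consent".

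Section 7c (Sample Size) allows for under 15% missing completion. It cites an earlier study in which "loss to follow-up was 2% with 7% mortality at 6 months", and continues: "thus, we expect 54 patients to complete the intervention". Under Hypothesis 1a, the same section repeats the study-level call measure in words, without the number 243. Completing at least 80% of intervention calls is one of the three feasibility criteria in that hypothesis.

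**The concern.** Once replacement starts, 27 per group is the number of patients with a 12-week assessment. It is no longer the number randomised. A BA-R patient who takes some calls and is then lost remains a study participant under section 4f, so those calls belong in a numerator that covers all participants. The nine calls intended for the additional patient are not in 243. Numerator and denominator then describe different groups, while the loss-to-follow-up measure in the same paragraph uses everyone enrolled.

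The error runs one way. It makes delivery look better, and it grows with the number of BA-R patients who have to be replaced, which is something a feasibility trial wants to see clearly. The rate could reach 80% when fewer than 80% of intended calls were made, and it could exceed 100%.

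**Working it through.** **Inputs.** Nine calls per patient: six weekly plus three two-weekly (section 7a). 27 BA-R patients (7a). Up to 10 additional patients (4a). Threshold 80% (Hypothesis 1a). Loss to follow-up 2% and mortality 7%, both at 6 months (7c). The number of additional patients randomised to BA-R, k, is not in the documents; it is assumed and varied.

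**The plan's own figure.** (6 + 3) × 27 = 243, which reproduces exactly. The pass mark is 0.80 × 243 = 194.4, so 195 calls.

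**Denominator with k extra BA-R patients.** Intended calls = 9 × (27 + k). Overstatement factor = 9(27 + k)/243 = (27 + k)/27.

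| k | BA-R patients | Intended calls | Factor | 195 calls as share of intended | Totals that pass on 243 only |
|---|---|---|---|---|---|
| 0 | 27 | 243 | 1.000 | 80.2% | none |
| 1 | 28 | 252 | 1.037 | 77.4% | 195–201 |
| 3 | 30 | 270 | 1.111 | 72.2% | 195–215 |
| 5 | 32 | 288 | 1.185 | 67.7% | 195–230 |

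The last column uses the pass marks on the full denominator: 0.80 × 252 = 201.6 (202 calls), 0.80 × 270 = 216, and 0.80 × 288 = 230.4 (231 calls).

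**An example at k = 1.** 198 completed calls read as 198/243 = 81.5%, but are 198/252 = 78.6% of those intended.

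**Which k is plausible**, if about half of the additional patients go to BA-R:

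- Replacing only the 2% lost: 54/0.98 = 55.1, so about 55 enrolled and k = 0 or 1.
- Replacing deaths as well (2% + 7%): 54/0.91 = 59.3, so about 59 enrolled and k = 2 or 3. Section 4a names only loss to follow-up as the trigger, so this is an assumption.
- At the 15% limit for loss: 9 of 63 is 14.3%, so k = 4 or 5. If all 10 extras replaced lost patients, loss would be 10/64 = 15.6%, which misses the loss criterion itself.

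The 2% and 7% are 6-month figures and may overstate 12-week loss.

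**Check against the per-patient measure.** Every BA-R patient has the same denominator of nine. The mean of the individual proportions over all BA-R patients is therefore total calls / [9 × (27 + k)]. This is the rate on the full denominator, and it does not involve the 27.

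**The case against.** The best reply is that the definition lies in the words, calls expected in the study, and that the bracket only evaluates it at the planned arm size. The Hypothesis 1a text repeats the words without 243, and an analyst could update both parts of the ratio to the actual enrolment. This stands in part: the wording in 7c does permit the right denominator. But 7a is the only place that puts a number on the expected total, it does so as a definition and not as an example, and nothing says that the number grows with replacements.

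A second reply is that the error would show. The mean per-patient proportion gives the figure on the full denominator, and the adherence measure in section 7b reports the proportion of sessions fully completed. An inflated study-level rate would disagree with both. This stands, and it is a main reason for calling the point minor.

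A third reply is that section 4f does not settle whether calls after death or withdrawal were still expected. That is true. Counting all nine for everyone randomised is a choice, but it matches the plan's own per-patient definition and its use of all enrolled patients for loss to follow-up.

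A reader might go further and infer that feasibility will be wrongly declared. The documents do not support that. They do not say whether the per-patient or the study-level proportion is compared with 80%, and no progression rule hangs on either.

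**Conclusion.** The point holds, conditionally, and is minor. If more than 27 patients are randomised to BA-R and 243 is applied as written, the study-level rate is too high by (27 + k)/27. The size rests on the assumed k: nothing at k = 0, 3.7% at k = 1 (about the most the 2% loss figure suggests), and up to about 18.5% at k = 5, roughly half of the 10 extras. A false reading of 80% or more needs a total inside a band: 195–201 of 252 calls at k = 1, a true rate of 77.4% to 79.8%. Outside the band, the rate is still overstated but falls on the same side of 80%.

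Two stronger readings should be avoided. One is that 9 × 27 is a miscalculation; it is correct for the planned 54 patients in equal arms. The other is that a large overstatement is to be expected; the larger values of k need deaths to be replaced or loss to approach the 15% limit. The efficacy analyses do not use this rate at all.

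**What to change.** In section 7a, and in the matching sentence under Hypothesis 1a in 7c, define total expected calls as nine times the number of patients randomised to BA-R, including those lost, withdrawn or replaced. Keep 243 only as the worked example for no replacements. It would also help to state which of the two call proportions is compared with 80%.

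This changes wording only and needs no new data. The one cost is that the reported rate may be slightly less favourable, because the calls intended for patients who were lost now count in the denominator.

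### Section 7c uses 54 both as patients enrolled and as patients completing, and the 10-patient top-up is missing from its total, its recruitment period and the 243-call denominator

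*Combined protocol and SAP*

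**What the plan says.** The number 54 appears in several roles.

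- **Section 7c, Sample Size, as enrolment:** "we aim to enroll a convenience sample of ~1.5 patients/month, for a total of 54 patients (based on 36 months of recruitment".
- **Same paragraph, on attrition:** "We expect an overall <15% missing completion rate due to mortality and loss to follow-up". A prior study by the group is cited with 2% loss to follow-up and 7% mortality at 6 months.
- **Same paragraph, as completers:** "thus, we expect 54 patients to complete the intervention". The detectable difference of 3.1 points on the Hospital Anxiety and Depression Scale (HADS) is then computed at 27 per group.
- **Section 7c, Hypothesis 2a, as the number left after attrition:** "sample size 54 (after accounting for mortality and loss to follow-up".
- **Section 4a, Overview of Research Methods:** 54 are to be enrolled, with a conditional top-up: "If patients are lost to follow-up, we will enroll up to 10 additional patients to obtain 12-week outcomes assessments". The stated aim is 54 assessed patients, 27 per group.

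For the primary feasibility outcome, Section 7a defines a pooled measure as the "total number of intervention phone calls completed by all study participants as a proportion of total intervention phone calls expected in the study", and fixes the denominator with an i.e.: "9 calls/patient x 27 intervention patients = 243 calls". Section 7c, Hypothesis 1a, repeats the measure without a number. The plan's feasibility thresholds are accrual of 1.5 patients per month, at least 80% of calls completed, and at most 15% "of enrolled patients lost to follow-up for outcomes assessments at end of the 12-week intervention".

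**The concern.** Read alone, the Sample Size paragraph moves from 54 enrolled, through an attrition allowance, to 54 completing, and joins the steps with "thus, we expect 54 patients to complete the intervention". No non-zero attrition permits that. The route that makes 54 completers possible is in another section and is not cross-referenced. As a result, the stated total and recruitment period describe a trial without the top-up, while the stated completers and power describe a trial with it.

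Two things depend on which is meant. The pooled call-completion proportion is part of the primary outcome, and its only stated denominator assumes exactly 27 patients in the behavioral activation-rehabilitation (BA-R) arm. The numerator covers all participants, so added BA-R patients could contribute calls without raising the denominator. The recruitment total and period are also what a reader would use to judge whether the trial can be delivered.

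**Working it through.** **Inputs.** Section 7c: 1.5 patients/month, 36 months, attrition under 15%, SD 4.2, 5% alpha (two-tailed under Hypothesis 1b), 80% power, 27 per group. Section 4a: up to 10 added patients. Section 7a: 9 calls per BA-R patient, 27 BA-R patients.

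**1. The plan's own products.** 1.5 × 36 = 54 and 9 × 27 = 243. Both reproduce exactly.

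**2. Completers if only 54 are enrolled.** Completers = 54 × (1 − attrition).
- At the 15% bound: 54 × 0.85 = 45.9, about 46.
- At 9%: 54 × 0.91 = 49.1, about 49. The 9% is 2% + 7% from the cited 6-month figures, so it is only an illustrative assumption for 12 weeks.

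**3. Enrolment needed for 54 completers.** Enrolment = 54/(1 − attrition).
- At 15%: 54/0.85 = 63.5, so 64, which equals 54 + 10.
- At 9%: 54/0.91 = 59.3, so 60.

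**4. Recruitment period or rate.** 64/1.5 = 42.7 months and 60/1.5 = 40 months, against 36 stated. Alternatively, 64/36 = 1.78 patients/month over the stated 36 months.

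**5. Pooled call proportion.** The smallest count reaching 80% of 243 is 195 (0.8 × 243 = 194.4). Suppose 195 calls are completed, top-up calls included.

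| BA-R patients allocated | Calls due | 195 as % of calls due |
|---|---|---|
| 27 | 243 | 80.2% |
| 28 (one top-up) | 252 | 77.4% |
| 32 (five top-ups, 1:1 assumed) | 288 | 67.7% |

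The overstatement arises only if 243 is kept while top-up calls are counted.

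**6. Detectable HADS difference.** Unadjusted, normal approximation: (1.960 + 0.842) × 4.2 × √(1/n₁ + 1/n₂). Power for 3.1 points is Φ(3.1/[4.2 × √(1/n₁ + 1/n₂)] − 1.960).

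| Completers | Per group | Detectable difference | Power for 3.1 |
|---|---|---|---|
| 54 | 27/27 | 3.20 | 77% |
| 49 | 25/24 | 3.36 | 73% |
| 46 | 23/23 | 3.47 | 71% |

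The first row is the plan's own scenario and does not give the stated 3.1. A t-based calculation gives 3.26. By the normal approximation, 3.1 points needs 29 per group.

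**The case against.** The strongest reply is that the protocol and analysis plan are one document, and Section 4a already deals with attrition. Its cap of 64 matches 54/0.85, and its target of 27 assessed per group agrees with the power sentence and with Hypothesis 2a. This stands. Three stronger readings that a reader might infer therefore fail.

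- **That the trial will end with only 46 to 49 completers and 71% to 73% power.** This holds only if the top-up is not used, which is not what Section 4a describes. The planned baseline-adjusted estimator may also do better than these unadjusted figures.
- **That recruitment must run to 43 months.** The documents do not make 1.5/month a ceiling, and about 1.8/month would deliver 64 in 36 months. The top-up is also conditional, so 64 is a maximum.
- **That the top-up undermines the retention criterion.** Using all 10 places to reach 54 gives 10/64 = 15.6% not completing, against 9/63 = 14.3% with nine. Missing a 15% limit at 15.6% is the criterion working as designed, since the formula divides by patients enrolled. Whether deaths count towards that limit is also open.

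It is also fair to say that the call measure is defined in words as calls expected in the study, and that nowhere does the plan say top-up calls would be set against 243. The distortion is therefore conditional. But 243 is introduced as the meaning of that phrase, not as an example, and it is the only number given.

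**Conclusion.** The point holds as a failure to align sections, not as a shortfall in the design. Section 7c cannot have 54 as both total enrolled and number completing. Section 4a's top-up makes 54 patients with 12-week outcomes reachable at attrition up to about 15%, but Section 7c's total and period and Section 7a's call denominator do not reflect it.

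The practical consequence is confined to the pooled call proportion. Near the 80% threshold, a single added BA-R patient can turn 77.4% into an apparent 80.2%, provided that 243 is kept and top-up calls are counted. The 67.7% figure also assumes that five of ten added patients go to BA-R. The per-patient call proportion (out of 9), the 1.5/month accrual criterion and the retention formula are unaffected.

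A separate and smaller matter is that the stated 3.1-point detectable difference is not what the plan's inputs give even at 27 per group. They give 3.2, with about 77% power for 3.1 (unadjusted, normal approximation).

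**What to change.** 1. **Section 7c, Sample Size.** State that 54 and up to 64 patients will be enrolled to obtain 54 with 12-week outcomes, and cross-reference Section 4a. Make the period or the rate consistent: up to about 43 months at 1.5/month, or about 1.8/month over 36 months. The choice is the sponsor's.
2. **Section 7a.** Define expected calls as 9 × the number actually allocated to BA-R, top-up patients included, with 243 as the example for 27. Use the same definition under Hypothesis 1a.
3. **Only if the top-up will not be used,** restate expected completers as about 46 to 49 and the unadjusted detectable HADS difference as about 3.4 to 3.5 points.
4. **Detectable difference.** Restate it as 3.2 points at 27 per group, or give the calculation that yields 3.1.
5. **Minor.** Say whether a death triggers a top-up: Section 4a names loss to follow-up only, while the 15% allowance in Section 7c also covers mortality. Under Hypothesis 1a, change the 12-month follow-up session to 12 weeks, to agree with Section 7a and the hypothesis itself.

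The cost is text edits, with no patients beyond the 10 already allowed. If the rate stays at 1.5/month, the stated period lengthens by up to about 7 months (43 − 36). Whether the timeline has room cannot be judged, because the timeline statement cited in Section 7c is not in the documents.
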